12. DATA AND SPECIMEN BANKING*

No specimens are being collected as part of the research. A limited data set will be securely stored for potential future use by the Principal Investigator. We acknowledge that we will be collecting address information which cannot be included in a limited data set. This information will be used to determine the social vulnerability index and then it will be removed from the study data set. The address information will not be stored for future use. A de-identified data set will be shared upon request in accordance with NIH requirements for data sharing.

13. Data Analysis and Management*

SAMPLE SIZE

For details related to sample size, please see #7 Study-wide Number of Subjects.

POWER ANALYSIS

Power calculations employ two-sided hypothesis testing, 80% power, 0.05 Type I error, and account for within-clinic clustering and between-clinic variation in size. If 25% of patients are unvaccinated at the start of the intervention and 5% of control-clinic patients go on to receive a

INVESTIGATOR STUDY PLAN - REQUIRED

vaccination during the intervention period, we can detect an intervention-control difference of 2.96%, i.e., 7.96% of intervention-clinic patients become vaccinated. This is consistent with the effect size of other studies using a similar approach.¹⁰⁻¹²

DATA ANALYSIS PLAN

The primary outcome of this study is receipt of a complete COVID-19 vaccination series (2 doses for vaccines that require 2 doses) among patients unvaccinated at a clinic's entry into the study, a binary outcome. We hypothesize that intervention-clinic patients receiving text messages from their provider will be more likely to receive a complete vaccination series than control-clinic patients. We will compare vaccination in patients from the two randomization arms using generalized linear mixed modeling,¹³ with a random effect for clinic to account for within-clinic clustering. In addition to estimating unadjusted between-randomization arm differences, we will adjust for key covariates, including study block as well as variables reflecting possible secular trends such as vaccine availability at the time of a clinic's entry into the study. Patient-level covariates will be available from the electronic health record (EHR), including age, sex/gender, insurance type, and address which will be used to determine the social vulnerability index; separate models also will adjust for race/ethnicity and relevant clinical diagnoses, both of which may be subject to more missing data than age and sex. In order to fully describe the population who did not receive the intervention (text messages), we will collect text communication preference, any responses to study text messages (to capture any patients responding "NO" to opt out of receiving further study text messages), and text delivery status (delivered/undelivered). We also will adjust for provider type (e.g., resident, attending, nurse practitioner) and time since last visit. In supplemental analyses, we will assess effect modification of the intervention-control difference by a) block, to explore whether intervention-control differences change over time; and b) provider type, to examine whether the impact of text message receipt varies by a patient's provider type. Analyses will be intention-to-treat.

Analyses for the secondary outcome of 1+ dose – also binary – will parallel the above analyses.

For the additional secondary outcome of racial/ethnic differences in vaccination rates, we will add an interaction between randomization arm and race/ethnicity to the above model. This will allow estimation of race/ethnic-specific vaccination rates in each arm and corresponding pairwise racial/ethnic differences in the intervention-control differences, as well as testing the statistical significance of this effect modification; we hypothesize that the beneficial impact of the intervention (versus control) will be larger in patients self-identifying as in minority racial groups than in patients self-identifying as white; that is, the gap in vaccination percentage between minority and non-minority patients will be smaller in the intervention arm.

Additional secondary analyses will estimate the percentage of intervention-clinic patients who initiate vaccination after the first provider text, after the second provider text, and after the third provider text. Related analyses will compare patients in each of these three subgroups with each other and with those not initiating vaccination after three texts, using generalized mixed models for categorical characteristics¹³ and linear mixed models for continuous characteristics such as age.¹⁴

DATA SECURITY

INVESTIGATOR STUDY PLAN - REQUIRED

All research staff collecting, or handling data will be trained in human subjects' procedures, confidentiality, and privacy protection. All investigators and project staff are required to receive and complete Human Subjects and HIPAA training. All research personnel will hold a current Human Subjects Training Certificate. Clinical staff will access data to send text messages to eligible patients, consistent with their role and current activities in the clinical system. They will provide a report of patients who the text messages were delivered to.

All Electronic Health Record (EHR) data pulls at UMMHC will be requested following the UMMS [Data Science Core](#) processes (currently located here: https://www.umassmed.edu/research-informatics/data_services/how-to-obtain-data/). We will follow institution-specific processes at the other clinic sites. We will transfer data from participating sites to UMMS using UMMS MoveIT to transfer the information securely. We will only transfer data after a data sharing agreement has been executed between the three organizations (UMMHC, EMKCHC, FHCW).

We are requesting a waiver of HIPAA authorization for the entire conduct of the intervention.

All computerized data will be kept on secured computers or network servers at Meyers Primary Care Institute/UMMS and/or the respective clinic sites. These data will be accessible only to research staff with approved access, using confidential usernames and passwords.

Patient participants will be assigned a numerical code (Study ID) for identification in study files. Names, addresses, and other direct identifiers will be removed from study data sets once data collection is complete and data accuracy is verified. The research data set used for study analysis will be a limited data set (containing only date and age identifiers); the Study ID will be retained for researcher communication about subjects.

Analyses will be performed using only limited data sets and only aggregate data will be reported. All data will be used for research purposes only; published data will not contain any individual identifiers and will be reported in the aggregate.

See also #14 Provisions to Monitor the Data to Ensure the Safety of Subjects, #26 Confidentiality and #27 Provisions to Protect the Privacy Interests of Subjects.

DATA MANAGEMENT

The study database will be programmed and maintained by study staff (e.g. Research Assistant, Project Manager, Principal Investigator). Handling and storage of all data will be conducted as described above under Data Security.

DATA QUALITY ASSURANCE

The PI of the study will be responsible for oversight of the clinical trial and will review study data on a periodic basis to monitor and ensure the safety of study subjects.

Data quality control will include regular data verification and protocol compliance checks by the PI and Project Manager. Reports detailing the study progress and subject status, any adverse

INVESTIGATOR STUDY PLAN - REQUIRED

events, and any protocol deviations will be generated and reviewed by the PI and additional study team members as necessary.

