7. STUDY-WIDE NUMBER OF SUBJECTS*

Patient Participants

The intervention will be implemented at approximately 16 primary care clinics selected from three healthcare systems, including UMMHC, the Edward M. Kennedy Community Health

INVESTIGATOR STUDY PLAN - REQUIRED

Center (EMKCHC), and the Family Health Center of Worcester (FHCW). Eligible patients seen at a study clinic are at least 18 years of age or older. Based on the most recent data, there were approximately 152,110 adult (age \geq 18) patients seen in the selected primary care clinics at UMMHC, EMKCHC, and FHCW.

Provider Participants

Eligible providers are those who currently work at one of the primary care clinics selected from the three healthcare systems (UMMHC, EMKCHC, FHCW). Using information available on each healthcare system's website, we estimated that there are approximately 250 providers employed across the selected primary care clinics who will be eligible to participate in the provider education portion of the intervention. We will collect data from a subset of these providers, covered in IRB docket #H00023125.

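### The supplemental arm-by-provider-type analysis allows for clustering by clinic but not by provider, so its standard errors are too small if outcomes correlate within provider

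*Combined protocol and SAP*

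**What the plan says.** Section 13, Data Analysis Plan, compares the arms by generalized linear mixed modelling "with a random effect for clinic to account for within-clinic clustering". No other random effect is named, and no cluster-robust variance is mentioned.

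Provider type enters twice. It is an adjustment variable: "We also will adjust for provider type (e.g., resident, attending, nurse practitioner) and time since last visit". It is also one of two effect modifiers in supplemental analyses: "provider type, to examine whether the impact of text message receipt varies by" that type. No separate model is given for the effect-modification analyses. The analyses of the 1+ dose outcome are to parallel those of the primary outcome.

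Section 7 gives the scale. For clinics: "The intervention will be implemented at approximately 16 primary care clinics selected from three healthcare systems". For providers: "we estimated that there are approximately 250 providers employed across the selected primary care clinics".

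Section 11 lets each provider in an intervention clinic decline texting for their patients or name individual patients to leave out. Section 13 says that analyses will be intention-to-treat, so those patients stay in the comparison.

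**The concern.** Provider type belongs to the provider. Within a clinic, the arm-by-provider-type term is informed by comparing groups of providers, so its precision depends on how many providers there are and how much they differ. A clinic intercept removes differences between clinics. It still treats patients who share a provider as independent once clinic is accounted for.

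The documents give reasons to expect some provider-level correlation. Providers may decline texting for their patients, attendance at the education session is voluntary, providers may stop the emails, and the prescription pads are used as each provider sees fit. Ordinary differences in counselling and patient mix add to this.

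At stake is a practical conclusion. The trial could report that texting works better for patients of one provider type when the data show only provider-to-provider variation. The bias runs one way: positive correlation makes the standard error too small.

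**Working it through.** **The plan's own figure.** The plan states a power figure only for the main comparison: a detectable difference of 2.96 points (5% vs 7.96%) at 80% power and two-sided 0.05. Without clustering, two proportions of 0.05 and 0.0796 need 1,085 patients per arm. The plan has 152,110 × 0.25 / 2 = 19,014 per arm, so the stated difference implies a design effect of 19,014 / 1,085 = 17.5. Neither the clinic ICC nor the variation in clinic size is given, so the figure can be neither confirmed nor refuted. With 38,028 / 16 = 2,377 patients per clinic, it back-solves to a clinic ICC of about 0.0070 for equal clinics and 0.0035 for a coefficient of variation (CV) of 1.0. This gives a sense of scale only and does not bound a provider ICC. The point below does not depend on it.

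**Inputs.** Adult patients 152,110, providers about 250 and clinics about 16 (Section 7); 25% unvaccinated at the start (Section 13, Power Analysis).

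- Unvaccinated patients: 152,110 × 0.25 = 38,028
- Per provider: m = 38,028 / 250 = 152.1
- Providers per clinic: 250 / 16 = 15.6

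**Formulas.** For a modifier that is constant within provider, analysed with a clinic effect only and equal panels:

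- Variance understated by DE = 1 + (m − 1) × ICC, where ICC is the within-clinic provider correlation
- Standard error used / correct standard error = 1 / √DE
- True type I error = 2 × [1 − Φ(1.96 / √DE)]

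Example at ICC 0.005: DE = 1 + 151.1 × 0.005 = 1.76; 1.96 / √1.76 = 1.48; type I error = 13.9%.

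| Provider ICC (assumed) | DE | SE used / correct SE | Type I error, formula | Simulated, equal panels | Simulated, panel-size CV 0.5 |
|---|---|---|---|---|---|
| 0.001 | 1.15 | 0.93 | 6.8% | 6.8% | 7.4% |
| 0.002 | 1.30 | 0.88 | 8.6% | 8.2% | 9.7% |
| 0.005 | 1.76 | 0.76 | 13.9% | 13.6% | 14.7% |
| 0.01 | 2.51 | 0.63 | 21.6% | 20.6% | 24.1% |
| 0.02 | 4.02 | 0.50 | 32.8% | 29.7% | 33.4% |

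The simulation used 16 clinics, 250 providers, two provider types, an event rate near 6.5%, no true interaction and 3,000 runs per setting. At a provider ICC of zero, the clinic-only test rejected in 5.4% (equal panels) and 4.6% (CV 0.5). When provider-level variation supplied the error term, through an analysis of provider proportions within clinics, rejection was 4.5% to 5.5% in every setting. A separate simulation (4,000 runs, 16 providers per clinic, 5 of them of the second type, 6% event rate) compared within-clinic contrasts between arms and rejected in 4.6%, 5.2% and 4.8% at ICC 0.005, 0.01 and 0.02.

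**Opt-out alone.** Assume that a share q of intervention providers declines and that their patients lose the full 2.96 points. The between-provider variance is q(1 − q) × 0.0296². Divided by 0.0796 × 0.9204 = 0.0733, it gives an ICC in the intervention arm of 0.0006 (q = 5%), 0.0011 (10%) and 0.0019 (20%). Control providers have no texts to decline, so their DE is 1 here. Weighting the two DEs by the arms' binomial variances:

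- q = 5%: (0.0733 × 1.086 + 0.0475) / (0.0733 + 0.0475) = 1.052, type I error 5.6%
- q = 20%: (0.0733 × 1.289 + 0.0475) / (0.0733 + 0.0475) = 1.175, type I error 7.1%

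**The case against.** The strongest reply is that the size of the problem is unknown. No provider ICC is given. The one mechanism that can be roughly sized from the plan's figures, opt-out, is small and acts in one arm only. The analysis is supplemental, with no stated hypothesis for provider type. The clinic random effect is stated for the arm comparison, and its use in the effect-modification model is inferred. All of this stands, and it limits the point to a conditional one. It does not remove it: the plan offers no other model for this analysis, and only a provider ICC of zero gives the right error rate.

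Three stronger readings are tempting, and the documents do not support them.

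- A reader might infer that the false-positive rate is 14% to 33%. Those figures need a provider ICC of 0.005 to 0.02, which nothing in the plan establishes. Lower values give 7% to 9%.
- A reader might infer that the primary result is compromised too. It is not, in this way: clinics are randomized, and the clinic effect already carries provider variation into the between-clinic comparison.
- A reader might infer that every text is signed by the provider, so that provider identity is already on file. Section 11 names the provider only where possible and otherwise the organization, and control clinics send no texts. Provider identity must come from the patient-provider link needed to assign provider type.

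**Conclusion.** The point holds in conditional form. As written, the arm-by-provider-type analysis, and its 1+ dose parallel, has standard errors that are too small if there is any positive provider correlation within clinics. With about 152 patients per provider, even small correlations count: type I error is about 7%, 9%, 14%, 22% and 33% at assumed ICCs of 0.001, 0.002, 0.005, 0.01 and 0.02. Opt-out alone would put it at about 6% to 7% under the stated assumption. Ordinary variation between providers would add to that by an amount the documents do not allow one to estimate.

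The conclusion rests on the clinic-only structure carrying over to the supplemental model and on the Section 7 and Section 13 counts. The change is worth making because it is cheap and removes an error of known direction. It does not threaten the trial's main conclusion.

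**What to change.** In the provider-type effect-modification model, and in the parallel 1+ dose model, add a random intercept for provider nested in clinic. Keep a coded provider ID in the analysis data set for both arms, taken from the same link that assigns provider type. Neither the EHR variable list in Section 11 nor the description of the analysis data set in Section 13 names such an ID, so it should be added there.

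State a fallback in advance in case the model does not converge: analyse provider-level summaries, or form clinic-level contrasts and compare them between arms. The plan gives three provider types as examples, so the contrasts should be made for each pair of types, using only clinics that have both. The simulations tested these two fallbacks and not the nested mixed model itself.

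The cost is wider confidence intervals in an exploratory analysis, one extra coded variable, and the loss of some clinics from some contrasts if that fallback is used. Design, randomization and the primary analysis stay as they are.

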14. PROVISIONS TO MONITOR THE DATA TO ENSURE THE SAFETY OF SUBJECTS*

The proposed study involves no more than minimal risk to participants. Therefore, we believe that an intensive data and safety monitoring plan is not needed. However, we will take steps to ensure the integrity of the data and to detect any adverse effects of the study on the participants.

See #16 for details related to the protection against risks to study subjects.

15. WITHDRAWAL OF SUBJECTS WITHOUT THEIR CONSENT*

Patient Participants

No patient participants will be recruited as there are no study-specific activities for them to engage in. As a result, there is no need to withdraw patient participants without their consent. No further text messages will be sent to patients who reply “STOP” to a text message.

Provider Participants

Provider participants will engage in a one-time education session and will receive approximately 4 emails with educational information about communicating with patients about COVID-19 vaccination. No further emails will be sent to any provider who asks not to receive further educational emails.

16. RISKS TO SUBJECTS*

Risk to Subjects

Patient participants

The proposed study poses minimal risks to patient participants. The risks that do exist are associated with potential loss of confidentiality.

Risks associated with potential loss of confidentiality

There is a slight risk that research records (EHR data) might be obtained by persons not authorized to do so. There is a slight risk that research data files might be compromised, and obtained or viewed by unauthorized persons. Our procedures for protecting against such risks are described below.

Provider participants

The proposed study poses minimal risks to provider participants. The risk that do exist are associated with participating in an educational session.

Risks associated with participating in an educational session

INVESTIGATOR STUDY PLAN - REQUIRED

Providers will be recruited to participate in a one-time education session. This activity can be time-consuming to complete and inconvenient to attend. Our procedures for protecting against such risks are described below.

Protections Against Risk for Patient and Provider Participants

Minimizing risks

The training and monitoring of all study staff performance in accordance with an IRB-approved study plan will be the responsibility of the Principal Investigator. All efforts will be made to minimize risks and participant inconvenience.

Protection for risks associated with potential loss of confidentiality

The organization proposing this study has systems, oversight, experienced personnel, and an organizational culture that supports the appropriate use, access and storage of confidential information. All persons collecting or handling data will be trained in human subjects' procedures, confidentiality and privacy protection. All investigators and project staff are required to receive and complete IRB and HIPAA training.

Data for all participants will be kept strictly confidential. All hard copies of research files will be kept in locked file cabinets or a locked file room. Participants will be assigned a numerical code (Study ID) for identification in the files. Names and other identifiers will be kept in separate locked files. Individual identifier information will be removed from study data files as soon as possible in the data processing steps. All computerized data will be kept on secured computers or networks. These data will be accessible only to research staff, using confidential usernames and passwords. Data sharing will only occur between sites with appropriate consent/waiver of consent, authorization/waiver of authorization, and an executed Data Use Agreement. Statistical analyses will be performed using only limited datasets and only de-identified data will be reported. All data will be used only for research purposes only; published data will not contain any individual identifiers.

Protection for risks associated with participating in an educational session

Providers will be recruited to participate in an education session. This can be time-consuming to complete and inconvenient to attend. We will minimize the inconvenience by offering to hold the education session at a convenient time for most providers of a given study clinic (e.g., lunch break) and via Zoom. Providers will be told that participation is voluntary and that participation in the study will have absolutely no bearing on their employment.

17. POTENTIAL DIRECT BENEFITS TO SUBJECTS*

It is uncertain whether individual participants will directly benefit from participation. Some participants may learn something new about vaccination (or specifically, about the COVID-19 vaccine). Some participants may be motivated to specifically discuss their concerns related to vaccination with their providers and/or patients. Some participants may become motivated to be vaccinated against COVID-19 which has substantial health

INVESTIGATOR STUDY PLAN - REQUIRED

benefits. Subjects may enjoy participating and may feel that doing so contributes to scientific knowledge in general.

18. VULNERABLE POPULATIONS*

Please refer to our answers to section #6 Exclusion and Inclusion Criteria.

We will not be targeting any specific vulnerable population for this study. Children and prisoners will not be included. It is possible that a pregnant woman may meet inclusion criteria and it is not an explicit exclusion criterion. However, the risks involved in participation are no more than risks typically associated with general care. While we are not providing COVID vaccinations as part of the study, we are promoting its use. Currently, there are no recommendations against vaccination for pregnant women. Further, PCPs can exclude patients from participation.

In the event of inclusion of pregnant women, the following three statements will hold true:

1. No inducements, monetary or otherwise, will be offered to terminate a pregnancy.
2. Individuals engaged in the research will have no part in any decisions as to the timing, method, or procedures used to terminate a pregnancy.
3. Individuals engaged in the research will have no part in determining the viability of a neonate.

While we will ask providers to participate in an education session and send them emails with brief educational content, providers will be informed that their decision not to participate or to unsubscribe from our mailing list will not impact their employment in any way.

